9.10.2 COVID-19 Symptoms

Each patient will record the following COVID-19 symptoms daily in the eDiary with the study-supplied devices (ie, tabloid, digital thermometer) through Day 14. For patients who are unable to complete the eDiary, the records of symptoms will be collected over the telephone.

- fatigue, chills, headache, cough (with or without sputum production), myalgia, sore throat, shortness of breath, nasal congestion, diarrhea, nausea or vomiting, and oral temperature.

The patient will be asked to grade the symptoms in scale of “not at all”, “a little bit”, “somewhat”, “quite a bit”, and “very much”.

A cumulative summary of the number and percentage of patients experiencing at least one symptom (as local, systemic, and overall) through Day 14 will be tabulated by maximum severity and treatment group. Differences between each NasoVAX cohort and pooled placebo for cumulative events (local, systemic, and overall) will be tested using Kruskal-Wallis tests. The number and percentage of subjects experiencing at least one grade of “quite a bit” and “very much” symptom through Day 14 days for each symptom type, as well as 95% Clopper Pearson exact CIs, will be presented by treatment group.

A summary of the number and percentage of subjects experiencing at least one event through Day 14 will also be tabulated by event type, maximum severity, and treatment group. In addition, a descriptive summary of the duration of events (regardless of severity) will be tabulated by event and dose group.

Generally, symptoms recorded in the eDiary and (unsolicited) AEs recorded in the AE log will be summarized separately. A change in symptoms from baseline will not be recorded as an (unsolicited) AE unless it meets the criteria of an SAE. Any event found in the AE log that is also captured in the eDiary will not be counted as an AE to avoid duplication.

9.10.3 *Safety Laboratory Tests and Vital Signs*

Clinical laboratory results will be listed for urinalysis. Presentations will use SI Units.

Observed and change from baseline of continuous clinical laboratory values will be summarized descriptively by each treatment group and visit. Summary statistics for continuous parameters will be presented by treatment group as follows: pre-treatment, post-treatment, and change from pre-treatment to post-treatment assessment.

The number and percentage of patients with post-treatment clinical laboratory values recorded as new abnormal (ie, an event with an increase in toxicity grade relative to the baseline value and with a severity grade of moderate [Grade 2]) or higher) after study treatment will be tabulated. Shift tables that cross-tabulate the pre-treatment and post-treatment clinical laboratory values of each patient by toxicity grades defined in Appendix 1 of protocol will be prepared.

Observed values and change from baseline of vital signs will be summarized descriptively at each time point by treatment group. The number and percentage of patients with post-treatment vital sign values recorded as newly abnormal (ie, an event with an increase in the toxicity grades [defined in Appendix 1 of the Protocol] relative to the baseline value) after study treatment will be tabulated. Individual vital signs data will be listed.

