### 5.2 Inclusion Criteria

Patients who meet all of the following criteria are eligible for participation in the study.

1. Able and willing to provide informed consent

Patients themselves must provide written informed consent before the performance of any study-related procedures, and surrogate consent by family members, designated legal representatives, or caregivers will not be permitted.

2. Men and women 18 years of age and older

3. Early COVID-19, defined as one or more symptom(s) of fever (oral temperature  $\geq 100.4^{\circ}\text{F}$ ), cough or shortness of breath, onset of these symptoms within 72 hours of screening, and confirmation of SARS-CoV-2 infection by a PCR-based or rapid antigen test diagnostic

4. Resting  $\text{SpO}_2 \geq 96.0\%$  on room air on two successive measurements

5. For women of childbearing potential (women who are not permanently sterile [documented hysterectomy, bilateral tubal ligation, salpingectomy, or oophorectomy], postmenopausal [12 months with no menses without an alternative medical cause] or in monogamous same-sex relationships)

- Negative urine pregnancy test at Screening
- Willingness to practice a highly effective method of contraception that includes, but is not limited to, abstinence, sex only with persons of the same sex, monogamous relationship with a postmenopausal partner, monogamous relationship with vasectomized partner, vasectomy, licensed hormonal methods, intrauterine device, or consistent use of a barrier method (eg, condom, diaphragm) with spermicide for 28 days after the last dose of study drug

6. For men with sexual partners of childbearing potential, willingness to practice a highly effective method of contraception, as defined above, for 45 days after the last dose of study drug

---

7. Ability and willingness to comply with all aspects of the study, including reliable internet access, through the entire study period

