  9. History of conditions associated with immunocompromise, including but not limited to poorly controlled HIV, or treatments known to affect the immune system, including but not limited to oral or intravenous corticosteroids, alkylating drugs, antimetabolites, cytotoxic drugs, radiation, immune-modulating biologics (including IL-6, IL-12, Janus kinase inhibitors or antagonists), and cancer treatments, within 30 days of Screening or anticipated use within 6 months following participation in this study
  10. Any medical, psychiatric, or social condition or occupational or other responsibility that in the judgment of the Investigator would interfere with or serve as a contraindication to protocol adherence, assessment of safety (including reactogenicity), or a patient's ability to give informed consent
-

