4.2 Schedule of Events

The schedule for study activities is presented in [Table 2](#).

Confidential

Table 2 Schedule of Events – Screening and Treatment Periods

Procedure	Study Visit Type / Day			
	Screening	Study Drug Treatment	Diary Completion/ Telephone Contact	Telephone Contact
	Study Center Visit		Remote Visit	
	Day 1 Pre-Dose	Day 1	Daily Days 1 to 14	Days 21 and 28 ±2 days
Informed consent	X			
Eligibility criteria check	X			
Demographics	X			
Medical history	X			
Focused cardiovascular and respiratory physical examination	X			
Height and weight	X			
Blood pressure and respiratory rate	X			
Urine pregnancy test ^a	X			
Randomization	X			
Study drug administration ^b		X		
Resting SpO ₂ ^c	X		X ^d	
Resting pulse rate ^c	X		X ^d	
Oral temperature ^c	X		X ^d	
Baseline/Concomitant medications	X		X	X
AEs			X	X
eDiary completion for COVID-19 symptoms ^e	X		X	
Criteria for the Assessment of Severity of Illness in Patients with COVID-19 ^f	X			X
Daily telephone contact to document concomitant medications, clinical and hospitalization status and AEs ^g			X	
Follow-up contact for hospitalization status, COVID-19 outcomes, and AEs ^h				X

^a For women of child-bearing potential only. Results must be available and confirmed to be negative before study drug administration.

^b Study drug is to be administered with the patient in the supine position. The patient is to remain in the supine position for 30 minutes thereafter and be observed for at least 2 hours post intranasal administration.

^c To be measured remotely daily at 09:00 and 16:00 hours or at any time the patient experiences worsening symptoms using the study-supplied devices and recorded in the eDiary. Resting SpO₂ and pulse are to be measured at rest for 2 minutes. A ±1 hour window will be allowed. On Day 1, only the afternoon (16:00 hours) measurement is required and may be measured at the study center or remotely.

^d If the Screening visit occurs in the morning, the patient will be responsible for recording the 16:00 measurements at home later that day; if the visit occurs after 16:00, measurements will commence at home the following morning.

Confidential

- ^e The following symptoms will be recorded: fatigue, chills, headache, cough (with or without sputum production), myalgia, sore throat, shortness of breath, nasal congestion, diarrhea, and nausea or vomiting.

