4.3 Study Population

Approximately 96 ambulatory patients with COVID-19, with onset of fever, cough, or shortness of breath within 48 hours and a confirmation of SARS-CoV-2 infection by a polymerase chain reaction (PCR)-based diagnostic within the prior 24 hours, will be enrolled at up to 5 study centers in the US.

The Inclusion and Exclusion Criteria of patients are provided in Protocol Sections 5.2 and 5.3, respectively.

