7 ADVERSE EVENTS

7.1 Definitions

7.1.1 Adverse Event

An AE is defined as any untoward medical occurrence associated with the use of a drug in humans, whether or not considered drug related. An AE can therefore be any unfavorable and unintended sign (including an abnormal laboratory finding), symptom, or disease temporally associated with the use of the investigational product whether or not related to the investigational product. An AE can be any sign, symptom, or diagnosis that appears or changes in intensity during the course of the study.

Unchanged chronic conditions are not AEs and should not be recorded on the AE pages of the eCRF. These medical conditions should be adequately documented on the appropriate page of the eCRF (medical history or physical examination). However, medical conditions present on the first day of treatment that worsen in intensity or frequency during the treatment or post-treatment periods in a manner not consistent with natural disease progression should be reported and recorded as AEs. The Investigator will actively solicit this information and assess the event in terms of severity and relationship to the study treatment regimen.

The objective of this study is to assess the effective and safety of NasoVAX in preventing clinical worsening of early COVID-19. The worsening of fever, cough, shortness of breath, resting SpO₂ or resting pulse rate, and symptoms of COVID-19 that are reported in the eDiary during Screening will be captured in aggregate in the eCRF and will not be reported as AEs.

The term AE is used to include any AE whether serious or not serious.

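### The overall at-least-one-symptom row in SAP 9.10.2 is nearly fixed by eligibility, and no symptom safety table is referenced to the Screening grade

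*SAP*

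**What the plan says.** SAP 9.10.2 (COVID-19 Symptoms) begins with "A cumulative summary of the number and percentage of patients experiencing at least one symptom (as local, systemic, and overall) through Day 14", to be tabulated by maximum severity and treatment group. Each NasoVAX cohort is compared with pooled placebo by a Kruskal-Wallis test. The section adds a per-symptom count of patients reaching either of the top two grades, with exact confidence intervals, a table by event type and maximum severity, and a summary of duration. The items counted are "fatigue, chills, headache, cough (with or without sputum production), myalgia, sore throat, shortness of breath, nasal congestion, diarrhea, nausea or vomiting, and oral temperature". None of these tables has a condition relating to the pre-dose grade.

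Eligibility (Protocol 5.2, criterion 3) requires "Early COVID-19, defined as one or more symptom(s) of fever", cough or shortness of breath, with onset within 72 hours of screening. SAP 4.3 still has "with onset of fever, cough, or shortness of breath within 48 hours". Patients are recently symptomatic under either version.

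On adverse events, SAP 7.1.1 says that worsening of symptoms "reported in the eDiary during Screening will be captured in aggregate in the eCRF and will not be reported as AEs". SAP 9.10.2 goes further. A change in symptoms from baseline is not an AE unless it is serious, and an AE-log event also captured in the eDiary is not counted as an AE.

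The schedule in SAP 4.2 marks "eDiary completion for COVID-19 symptoms" in the pre-dose Screening column as well as daily through Day 14.

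**The concern.** The symptom tables have the layout of a reactogenicity summary for healthy vaccine recipients: any symptom, local or systemic, by maximum severity. Here the recipients are already ill with the symptoms being counted. An overall any-symptom percentage close to its ceiling in both arms cannot separate them. Maximum grade and duration through Day 14 partly reflect how ill the patient was at entry and how the infection ran its course.

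Elsewhere the SAP uses a baseline reference. A treatment-emergent AE must be new or worsened (9.10.1), and newly abnormal laboratory or vital-sign values must show a rise in grade from baseline (9.10.3). The symptom tables are the exception. They are also where non-serious symptom changes end up, because 9.10.2 takes them out of the AE counts.

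Safety and tolerability is a stated objective (Protocol 2.2, SAP 2.2). If an intranasal dose produced, say, nasal congestion or sore throat in the first days, no planned safety table would give the number of patients in each arm in whom that symptom was new or worse after dosing.

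**Working it through.** The documents give no expected symptom rate or power for these tables, so there is no planned figure to reproduce. Arm size is 10 + 14 + 24 = 48 (SAP Table 1). All symptom rates below are assumptions. Powers are for 48 versus 48 at two-sided 0.05, because SAP 9.10.2 states no level.

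**1. Overall any-symptom row.** The entry symptoms are fever, cough and shortness of breath. The 9.10.2 list contains cough, shortness of breath and oral temperature, so eligibility drives the overall count towards 100%. With NasoVAX set to its maximum of 100%, exact Fisher power is:

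| Placebo any-symptom rate | Power |
|---|---|
| 90% | 35% |
| 95% | 3% |
| 98% | 0.04% |
| 100% | 0 |

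Suppose instead that the drug causes a symptom in 30% of patients independently of disease, and placebo is at 95%. NasoVAX is then at 1 − 0.05 × 0.70 = 96.5%, and power is under 1%.

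**2. Maximum-severity split.** Assume that everyone is symptomatic, with placebo maximum grades split 20/30/30/20% over the four non-zero grades. Move a fraction f of NasoVAX patients up one grade, with the top grade capped. The any-symptom share stays at 100%. The top-two-grade share becomes 0.50 + 0.30f. Kruskal-Wallis power is by simulation (3,000 runs).

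| f | Top two grades, NasoVAX (placebo 50%) | Power |
|---|---|---|
| 30% | 59% | 20% |
| 50% | 65% | 48% |
| 100% | 80% | 98% |

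The severity tables therefore do not share the ceiling. However, the SAP's own test sets NasoVAX cohorts of 10, 14 or 24 against pooled placebo. Those groups are smaller, and the placebo patients come from cohorts with different age and risk criteria.

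**3. Contrast for one symptom.** If the placebo rate is b and the drug independently causes the symptom in a fraction q, the NasoVAX rate is 1 − (1 − b)(1 − q), and the gap is q(1 − b). With q = 20%:

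| Table | Placebo b | NasoVAX | Gap |
|---|---|---|---|
| Cumulative through Day 14 | 60% | 1 − 0.40 × 0.80 = 68% | 8 points |
| New or worse, early window | 10% | 1 − 0.90 × 0.80 = 28% | 18 points |
| New or worse, early window | 30% | 1 − 0.70 × 0.80 = 44% | 14 points |
| New or worse, early window | 50% | 1 − 0.50 × 0.80 = 60% | 10 points |
| New or worse, early window | 60% | 1 − 0.40 × 0.80 = 68% | 8 points |

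Fisher power is about 9% for 68% versus 60%, and about 52% for 28% versus 10%. With a larger effect, q = 30%, a new-or-worse count has power of 85%, 65%, 47% and 25% at placebo rates of 10%, 20%, 30% and 50%.

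**The case against.** A reader might infer that the symptom tables cannot show NasoVAX tolerability at all. The documents do not support that. The sentence that sets up the any-symptom count also splits it by maximum severity, and step 2 shows that a grade shift can appear with everyone symptomatic. The per-symptom, event-type and duration tables can differ too. The ceiling applies to the overall row. The SAP does not say which symptoms are local or systemic, so nothing forces those rows to 100%. Nor is the ceiling exact: the criterion concerns onset before screening, and a symptom such as fever may have resolved before dosing.

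A reader might also infer that these tables are the only place where a dose reaction could appear. That is not so either. SAP 9.9.2 plans an MMRM of change from Baseline in eDiary symptoms, with day and treatment-by-visit terms. Oral temperature and antipyretic use are separate safety endpoints (SAP 3.3). Vital signs are summarised as change from baseline, and all reported AEs are listed. What stands is narrower: the MMRM sits under efficacy and does not give the number of patients with a new or worse symptom, and the other routes do not cover terms such as nasal congestion or sore throat in a comparative count.

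The protocol's phrase "assessment of safety (including reactogenicity" comes from an investigator-judgement exclusion criterion. It does not create a reactogenicity endpoint, and eDiary symptoms are not listed among the safety endpoints.

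Finally, the gain from a baseline-referenced table depends on the placebo worsening rate. These patients are within days of symptom onset, so early worsening may be common. At 60% placebo worsening the gain disappears. This objection stands in full and limits what the fix can deliver.

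**Conclusion.** The point holds in a limited form. The overall any-symptom percentage is close to uninformative by design. The remaining symptom safety tables can show an arm difference but cannot say how much of it was already present at entry, because none uses the Screening grade. The AE counts do not fill the gap, since SAP 9.10.2 removes non-serious symptom changes and events duplicated in the eDiary.

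The near-100% figure follows from eligibility and the item list; the exact level is not known. The gain from the fix, 8 points rising to between 10 and 18, rests on an assumed 20% drug effect independent of disease, 60% cumulative placebo incidence and 10% to 50% early placebo worsening. The study is exploratory and was not sized for significance, so the case rests on whether the table is interpretable. It does not rest on a power target. The documents do not support concluding that the plan would necessarily miss a tolerability problem.

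**What to change.** Add to SAP 9.10.2 a per-symptom table, by randomised arm, of patients whose post-dose eDiary grade exceeds their Screening eDiary grade, together with the maximum increase in grade. Show it for an early post-dose window, fixed before unblinding, and for the rest of the period through Day 14. Keep the planned cumulative and severity tables beside it as descriptive summaries.

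Confirm that the five-point Screening grade is recorded before dosing. The schedule and SAP 7.1.1 indicate an eDiary at Screening. However, SAP 4.1 mentions eDiary instructions only as something provided before discharge on Day 1, and Protocol 9.1.1 ties Screening symptoms to the medical history in Section 8.1.2, which does not mention that scale.

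The cost is SAP wording, table shells and a few more rows. The window cut-point is a convention. Patients already at the top grade at Screening cannot increase, so their number should be shown for each symptom. The contrast weakens as early worsening on placebo becomes more common.

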2.2 Safety

- To assess the safety and tolerability of NasoVAX in patients with early COVID-19

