Upon signing informed consent, patients will undergo Screening assessments at the study center, as per the Schedule of Events ([Table 2](#)). Within each cohort, patients who are determined to be eligible will be randomized that same day (Day 1) in a 1:1 ratio to receive either NasoVAX or placebo with approximately 10 and 14 patients in Cohorts 1 and 2, respectively, receiving NasoVAX and 10 and 14 receiving placebo in Cohorts 1 and 2, respectively ([Table 1](#)). Approximately 24 patients will receive NasoVAX and 24 will receive placebo in Cohort 3. Randomization in Cohort 2 will be stratified by age groups of 35-64 years and 65 years and above. Randomization in Cohort 3 will be stratified by age groups (ages 35-64 years, ages 65 and above) and co-morbidity (one or more risk factors present, no risk factors present). Enrollment of patients ages 35-49 will not exceed approximately 30% of the randomized population of either treatment arm.

Table 1 Study Design

Cohort	Cohort Description	Number of Doses	NasoVAX Dose (vp)	Number of patients	
				NasoVAX	Placebo
1	Ages 35-49 years and risk factors disallowed	Single	1 x 10 ¹¹	10	10
2	Ages 35 and above and risk factors disallowed	Single	1 x 10 ¹¹	14	14
3	Ages 35 and above and risk factors allowed	Single	1 x 10 ¹¹	24	24
Group Total				48	48
Study Total				96	

Study drug will be administered as a single intranasal dose of 0.5 mL (0.25 mL each nostril) in the supine position after which patients must remain in the supine position for 30 minutes. Patients will be observed for at least 2 hours post intranasal administration. Patients who are randomized will be considered enrolled in the study.

No in-person visits are expected during the study after Day 1 unless a participant experiences a change in symptoms or AE that requires a visit for assessment.

Prior to discharge from the study center on Day 1, patients will be provided with:

- A fingertip pulse oximetry device that connects to a mobile device connecting to a tablet that will be supplied to the patient to measure resting SpO₂ and resting pulse rate remotely. Patients will be trained on the use of the device and tablet.
- A digital thermometer for measurement of oral temperature
- Instructions regarding how to take the above measurements and access and complete a web-based electronic diary (eDiary)

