9.4 Sample Size

The study is considered exploratory to assess the initial safety of NasoVAX in COVID-19 and response to treatment. The sample size chosen for this study was considered adequate to meet the study objectives and was selected without statistical significance considerations.

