9.9 Analysis of Efficacy Data

Efficacy analyses will be conducted using the mITT and PP Populations with the primary conclusions drawn from the mITT Population. Placebo will be the collective (pooled) across cohorts.

Descriptive statistics will be used to evaluate differences between Baseline and post-Baseline efficacy endpoints. The study is considered exploratory, and inferential statistics will be employed as appropriate.

For the purpose of study efficacy endpoints, resting SpO₂ and resting pulse rate will be assessed on observed data only; if data is missing, it will not be imputed.

The p-values from significance tests will be obtained at a one-sided significance level of 0.025.

No multiplicity adjustments will be made for the efficacy endpoints.

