9.10 Analysis of Safety Data

Quantitative safety data, including the frequencies of AEs, oral temperatures, use of antipyretics and bronchodilators, and length of hospital and ICU stay, will be summarized using descriptive statistics and frequency distributions. Qualitative safety data will be summarized by frequencies and percentages. All summaries will be presented by overall NasoVAX, NasoVAX cohort, and pooled placebo groups. AEs will be coded using the latest version of MedDRA, and severity will be coded using the latest version of the CTCAE, v.4.0.3. Concomitant medications will be coded using the latest version of the World Health Organization (WHO) drug dictionary. Safety comparisons will be made by treatment group and include comparisons for cohort or stratification factors (ages 35-64 years vs. ages 65 years and above, one or more risk factors present vs. no risk factors present).

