9.10.1 Adverse Events

All AEs recorded on the AE eCRF during the study will be coded to SOC and PT using the most current version of MedDRA, currently MedDRA 20.1.

A treatment-emergent AE (TEAE) is defined as an AE that was not present prior to treatment with IP, but appeared following treatment or was present at treatment initiation but worsened during treatment. An AE that was present at treatment initiation but resolved and then reappeared while the patient was on treatment is a TEAE (regardless of the intensity of the AE when the treatment was initiated). Programmatically, an AE will be classified as a TEAE if the start date and time occurs on or after the start date and time of first IP dosing.

All reported AEs will be listed, but only TEAEs will be summarized.

The overall incidence of TEAEs (number and percentage of patients, 95% CI) as well as the number of events will be summarized by treatment group, intensity as assessed by the latest version of National Cancer Institute's Common Terminology Criteria for AEs, SAE, related TEAE, TEAEs leading to study or investigational product discontinuation, and SAEs resulting in death.

The number (percentage, 95% CI) of patients with AEs from Day 1 to Day 42 (including SAEs) will be summarized for each MedDRA system organ class and PT and by treatment group. The number (percentage) of patients with SAEs from Day 1 to Day 210 will be summarized in a similar fashion. The number (percentage, 95% CI) of patients with AEs by severity and by relationship to IP will also be summarized.

The TEAEs will be summarized and tabulated at both the patient (n [%] of patients) and event (number of events) level for each treatment group and overall as follows:

- SOC and PT
- SOC, PT, and maximum reported severity
- SOC, PT, and maximum relationship to investigational product

Subjects with SAEs will also be summarized by SOC and PT for each treatment group and overall.

For the incidence at the patient level by SOC and PT, if a patient experiences more than 1 event within the same SOC and PT, only one occurrence will be included in the incidence.

For the incidence at the patient level by SOC, PT, and severity, if a patient experiences more than 1 event within the same SOC and PT, only the most severe occurrence will be included in the incidence.

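### SAP 9.10 names one between-group safety method, a cohort-versus-pooled-placebo Kruskal-Wallis p-value, and plans no interval for a NasoVAX-minus-placebo difference in AEs or symptom proportions

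*SAP*

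**What the plan says.** The safety objective is "To assess the safety and tolerability of NasoVAX in patients with early COVID-19" (SAP 2.2); the protocol's Study Summary labels it the primary safety objective. SAP 9.10 announces that "Safety comparisons will be made by treatment group and include comparisons for cohort or stratification factors" but names no test or estimator for this.

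The one method given is in 9.10.2, for symptoms accumulated through Day 14: "Differences between each NasoVAX cohort and pooled placebo for cumulative events (local, systemic, and overall) will be tested using Kruskal-Wallis tests". The same section tabulates maximum severity by treatment group and gives Clopper-Pearson intervals, by group, for the percentage with a grade of quite a bit or very much. For adverse events, 9.10.1 gives overall TEAE incidence with a 95% CI and adds: "The number (percentage, 95% CI) of patients with AEs by severity and by relationship to IP will also be summarized". These intervals are all for single groups.

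Group sizes are in SAP 4.1: "with approximately 10 and 14 patients in Cohorts 1 and 2, respectively, receiving NasoVAX and 10 and 14 receiving placebo", and "Approximately 24 patients will receive NasoVAX and 24 will receive placebo in Cohort 3". The sample size "was selected without statistical significance considerations" (SAP 9.4). A test level appears only in the efficacy section: "The p-values from significance tests will be obtained at a one-sided significance level of 0.025" (SAP 9.9).

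**The concern.** Three features of the stated method limit what it can say about safety.

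- A Kruskal-Wallis test yields a p-value and no estimate. It does not show how large a symptom excess the data leave open.
- Each comparison uses only part of the NasoVAX arm.
- Randomization was within cohort. Comparing one cohort with placebo pooled over three cohorts mixes the drug effect with differences in age and risk factors between cohorts.

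The symptom analysis matters more than usual here. Worsening of COVID-19 symptoms reported at Screening is not an AE (SAP 7.1.1). Hospitalization due to such worsening is not an SAE (SAP 7.2). Diary events that also appear in the AE log are not counted as AEs (SAP 9.10.2). If an intranasal product aggravated congestion, sore throat or cough, the AE tables would largely not show it.

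**Working it through.** **Inputs from the SAP.** NasoVAX n = 10, 14 and 24; placebo n = 10 + 14 + 24 = 48 when pooled; symptoms graded on five levels. The plan states no effect size or power, so there is no power figure of its own to reproduce. The allocation is consistent: 48 + 48 = 96.

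**Assumptions, not in the documents.** A worsening of 0.5 SD on the scale underlying the grades; two-sided 0.05 (for two groups, the same critical value in the harmful direction as one-sided 0.025); several five-level grade distributions.

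**Step 1: miss rate, normal approximation.** SE = sqrt(1/n + 1/48) in SD units; power = Φ(0.5/SE − 1.96).

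- n = 10: SE 0.348; Φ(1.438 − 1.96) = 0.30; missed 70%
- n = 14: SE 0.304; Φ(1.646 − 1.96) = 0.38; missed 62%
- n = 24: SE 0.250; Φ(2.000 − 1.96) = 0.52; missed 48%
- n = 48: SE 0.204; Φ(2.449 − 1.96) = 0.69; missed 31%

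**Step 2: the rank test itself.** Multiplying the effect by sqrt(3/π) allows for rank-test efficiency. The other rows are simulated.

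| Missed, versus 48 placebo | n = 10 | n = 14 | n = 24 | n = 48 |
|---|---|---|---|---|
| Rank-efficiency adjusted | 71% | 64% | 50% | 33% |
| Kruskal-Wallis, no ties | 72% | 65% | 51% | 34% |
| Kruskal-Wallis, five levels | 72–80% | 67–73% | 52–60% | 36–41% |

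Over the three cohorts this is 50–72% without ties and 52–80% on a five-level scale. The n = 48 column is a comparison the SAP does not plan with this test.

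**Step 3: a binary version.** If 20% on placebo and 40% on NasoVAX have a top-two grade (assumed rates), exact two-sided Fisher power against 48 placebo patients is 23%, 28% and 38% for n = 10, 14 and 24, and 49% for 48 versus 48.

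**Step 4: the pooled comparator.** Cohort 3 supplies 24/48 = 50% of pooled placebo. Suppose its placebo patients are 0.5 SD more symptomatic than those in Cohorts 1 and 2 (assumed). The pooled placebo mean then sits 0.5 × 0.5 = 0.25 SD above the Cohort 1 and 2 placebo level.

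- A true 0.5-SD harm in Cohort 1 or 2 appears as 0.5 − 0.25 = 0.25 SD. Approximate power is Φ(0.25/0.348 − 1.96) = 0.11 in Cohort 1 and Φ(0.25/0.304 − 1.96) = 0.13 in Cohort 2. Simulated on five levels it is about 8–11%.
- With no drug effect, Cohort 3 NasoVAX would look 0.25 SD worse than pooled placebo. The chance of a significant result in that direction is about Φ(0.25/0.250 − 1.96) = 0.17 instead of 0.025.

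Pooling can therefore hide harm in Cohorts 1 and 2 and suggest it in Cohort 3. Using each cohort's own placebo removes the bias but costs precision: with SE = sqrt(2/n), the miss rates in Step 1 become 80%, 74% and 59%. This is the reason to combine within-cohort differences over all 96 patients.

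**Step 5: what an overall difference would show.** The approximate 95% half-width for 48 versus 48 is 1.96 × sqrt(p(1 − p) × 2/48): 12, 18 and 20 percentage points at assumed proportions of 10%, 30% and 50%. With 0/48 in both arms, the Newcombe upper limit is +7.4 points.

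**The case against.** The strongest reply is that the plan contains more comparison than section 9.10 suggests. SAP 9.9.2 fits an MMRM to the same eDiary symptoms with a treatment effect and the stratification factors. SAP 9.9.1 plans score intervals for differences in hospitalization by oxygen level, and 9.9.4 plans intervals for LS-mean differences in SpO2 and pulse rate. This stands: a reader might infer that symptoms are never compared over the whole trial, or that the SAP has no difference interval anywhere, and both would be wrong. What remains is narrower. The MMRM is filed under efficacy with no symptom score defined and no difference interval named. The 9.9.1 intervals again set single cohorts against pooled placebo. None of these covers AEs or symptom proportions.

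A reader might also infer that a non-significant test will be reported as showing that NasoVAX is tolerated. The documents do not say so. They call the study exploratory, and cohort progression rests on DMC review and stopping rules.

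The eDiary symptoms are collected under efficacy assessments and are not in the safety endpoint list (SAP 3.3). That is fair, but the SAP places this test under safety analysis, and its AE rules leave symptom worsening largely to that analysis.

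Finally, the within-group intervals and counts already show imprecision and direction, and anyone can compute a difference from pooled counts. That holds for a crude difference. A cohort-stratified difference needs NasoVAX and placebo counts within each cohort, and the SAP pools placebo.

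**Conclusion.** The concern holds for section 9.10. Its one named between-group method gives no estimate, compares groups that were not randomized against each other, and under the stated assumptions misses roughly half of 0.5-SD harms in Cohort 3 and about 70% to 80% in Cohort 1. The 50–80% range depends on the assumed shift, test level and grade distributions. It models a single generic grade, whereas the SAP tests local, systemic and overall categories without assigning symptoms to them. The missing effect estimate and the non-randomized comparator do not depend on those assumptions; the masking figures depend on an assumed 0.5-SD difference between placebo cohorts.

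This does not invalidate the trial. Nor would an interval make it sensitive: half-widths of 12 to 20 points remain. A reader might therefore want tolerability judged by the upper confidence limit, but the documents give no margin, so that would not be a usable rule. The gain is a randomized, whole-trial estimate whose imprecision is visible.

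**What to change.** - **SAP 9.10.2:** make the main comparison the overall NasoVAX-minus-placebo difference, stratified by cohort, in the proportion of patients with at least one grade of quite a bit or very much, for each symptom, with a 95% CI.
- **SAP 9.10.1:** add the same stratified difference and 95% CI for any TEAE, grade 3 or higher TEAE, related TEAE and SAE.
- **By-cohort results:** keep them descriptive, with each cohort's own placebo group shown. If a Kruskal-Wallis or other rank test is kept, make it within cohort or stratified by cohort.
- **SAP 9.10:** state that a non-significant p-value is not evidence of no harm.

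The cost is SAP wording and a few table columns from a stratified risk difference, with no new patients or data. The downside is wide intervals, which show how little harm 96 patients can exclude.
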